9.4.3. Efficacy Analyses

9.4.3.1. Primary Analysis

The primary analysis for the Broad Panel Cohort will be conducted approximately 6 months after the first dose of the last Broad Panel Cohort subject (reaching approximately 200 response-evaluable subjects) and the analysis will be based on Treated Population in the Broad Panel Cohort.

The primary efficacy analysis will be performed on the pooled data of all tumor histologies that did not meet the futility for the Treated Population in the Broad Panel Cohort and the Core Panel Cohort. The primary endpoint ORR (CR or PR) according to RECIST v1.1 or RANO criteria assessed by the IRC will be calculated with 95% 2-sided exact CI. Statistical inference on ORR by IRC will be tested at 0.025 one-sided level, unless otherwise specified. To adjust for multiplicity, an error-spending function approach (Spiessens 2010) will be used to split the significance level using the observed size of the Core Panel Cohort relative to the size of the Broad Panel Cohort.

Refer to the SAP for details of the supplementary and sensitivity analyses.

Other efficacy analyses that will be focused on the Broad Panel Cohort and the Core Panel Cohort include:

- ORR (CR or PR) according to RECIST v1.1 or RANO criteria assessed by the investigator will be calculated with 95% 2-sided exact CI
- The distributions of DOR will be summarized using Kaplan-Meier estimates based on responding subjects. The estimated median will also be reported along with a 95% CI
- DCR and CBR will be calculated with 95% 2-sided exact CI
- PFS and OS will be summarized using similar Kaplan-Meier methods

Safety and efficacy analyses will be conducted on the Cholangiocarcinoma Expansion Cohort and the Exploratory Cohort at the same time as the primary analysis of the Broad Panel Cohort.

Primary Analysis for the Pediatric Cohort

The treated subjects (approximately 20) who have either progressed following prior therapies and who have no acceptable standard therapies in the proposed Pediatric Cohort (including the adolescent subjects enrolled in the Broad Panel Cohort) will be the primary analysis population for the Pediatric Cohort. The additional approximately 6 subjects who have a newly diagnosed solid tumors and who have no acceptable standard therapies will be analyzed separately from the Broad Panel Cohort.

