5.2.3. Analysis Methods

5.2.3.1. Primary Analysis

Before the primary efficacy test, a final futility assessment using the same futility guideline at the interim analysis (i.e, $\text{Pr}(\text{ORR} > 25\%) < 40\%$) will be conducted for all enrolled tumor histologies to identify the tumor histologies for the pooled primary efficacy analysis. This futility assessment takes into consideration the possibly enrolled new subjects in tumor histologies after Interim III, as well as more available information of the subjects that continue treatment and become evaluable in the early futile tumor histology groups. All available data (eg, efficacy, safety, and biomarker data) will be assessed by the DRC to determine whether a given tumor histology is futile. The primary efficacy analysis after the final futility assessment will be performed on the pooled data from all tumor histologies that didn't meet futility in this final futility assessment for the Treated Population in the Broad Panel Cohort and the Core Panel Cohort.

The null hypothesis of $H_0: ORR \leq 15\%$ will be tested at a significant level of 0.025 using one-sided exact binomial test. The test will be performed on the pooled data of all tumor histologies that didn't meet the futility criteria in the Broad Panel Cohort. An additional test will be performed on the pooled data from all tumor histologies that didn't meet the futility criteria in the Core Panel Cohort as mentioned in Section 0.

The ORR assessed by IRC and its two-sided 95% Clopper-Pearson CI will also be provided.

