Alternative	0.35	0.35	0.35	0.35	0.35	0.35	0.35	0.35	0.35	0.35	0.35	0.35	0.35	0.35	0.35	0.35
Target	0.25	0.25	0.25	0.25	0.25	0.25	0.25	0.25	0.25	0.25	0.25	0.25	0.25	0.25	0.25	0.25
Half-Half	0.10	0.10	0.10	0.10	0.10	0.10	0.10	0.35	0.35	0.35	0.35	0.35	0.35	0.35	0.35	0.15
Other35																
Half-Half	0.10	0.10	0.10	0.10	0.10	0.10	0.10	0.35	0.35	0.35	0.35	0.35	0.35	0.35	0.35	0.14
Other15																
Cholangio35	0.10	0.10	0.15	0.15	0.35	0.15	0.15	0.15	0.15	0.15	0.15	0.15	0.15	0.15	0.15	0.14

Note: Bold indicates the active (ORR>15%) tumor histologies; no bold represents the nonactive (ORR≤15%).

A.3.2. Definitions of Operating Characteristics

The following terminology will be used to discuss operating characteristics of the BHM analysis.

Selection Power

Selection power is the proportion of simulations that selected at least a given percentage of active tumor histologies (e.g. 80%) to be pooled for the primary efficacy analysis.

Proportion of Success

Proportion of success is the proportion of simulations in which BHM claimed at least one tumor histology as a success. Similarly, the success criteria ($\text{Pr}(\text{ORR} > 25\%) > 80\%$) is used for BHM to claim a success (efficacy) for a given tumor histology.

Family-wise Error Rate (FWER)

FWER represents the proportion of simulations in which BHM claimed false-positive efficacy in one or more of the nonactive tumor histologies. Note that the success criteria ($\text{Pr}(\text{ORR} > 25\%) > 80\%$) is used for BHM to claim a success (efficacy) for a given tumor histology.

The following terminology is used to discuss the exact binomial test in the pooled primary efficacy analysis.

Power

Power is calculated as the proportion of simulations claiming a success (efficacy) on the pooled data of primary efficacy analysis.

False Positive Rate (FPR)

FPR is defined as the proportion of simulations claiming a false-positive success (efficacy) on the pooled data of the primary efficacy analysis. Note that a success is false-positive only when the weighted average of true ORRs is less than 15% for the remaining histologies that didn't meet the futility criteria in the pool for primary efficacy analysis. The weights are the renormalized assumed prevalence in [Table A1](#) for each tumor histology that ended up in the pool.

Mixing Nonactive

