Mixing nonactive is defined as the proportion of claiming a success (efficacy) in the pooled data at the primary efficacy analysis that is mixed with at least one nonactive histology.

A.3.3. Operating Characteristics Results

20000 simulation runs were conducted to evaluate the operating characteristics of the proposed design.

Selection Power under The Alternative Scenario (Sample Size Determination)

The selection power under the Alternative scenario was used for sample size determination. As mentioned in section 1.4., the sample size of 200 response-evaluable subjects for the Broad Panel Cohort is justified based on extensive simulations with various Bayesian hierarchical model (BHM) designs to achieve approximately 80% power to select at least 80% tumor histologies (e.g., ≥ 12 of 15 tumor histologies) in the Alternative scenario (true ORR at 35% for all histologies). The selection power for Alternative scenario under the proposed design is shown in [Figure A3](#). The probability of selecting more than 12 active histologies for the pooled primary analysis is approximately 83%; the probability of selecting at least 10 active histologies is approximately 95%; the probability of selecting all 15 active histologies groups dropped to 29.4%.

[figure not shown]

Figure A3: Selection Power for Alternative Scenario

Power and Proportion of Success

The power based on pooled efficacy analysis and the proportion of success based on BHM are listed in [Table A3](#) for all scenarios. Note that the proportion of success and the power in the first row of Global Null represent the FWER and FPR and will be discussed the next. The design is achieving above 99% power and proportion of success for scenario Alternative; For scenario Target, it achieves above 95% while has a moderate proportion of success of 70%; The scenario Half-Half Other35 achieves 99% power and 94% proportion of success; The power and proportion of success for the scenario Half-Half Other15 are approximately 98% and 87%; The power and proportion of success for scenario Cholangio35 are lower than 50%, note that if the ORR for Cholangio is 50% with other ORRs remaining the same, the power and proportion of success will increase to approximately 83% and 77% respectively (not listed as one scenario).

Duration of the Trial

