It is shown that the FPR for pooled analysis is around 18.57% for Global Null scenario. Among the false positive cases, there are 16.34% false positive cases that include group Other that did not have interim futility analyses, and 36.7% false positive cases that include at least 1 group with less than 5 subjects. For the Half-Half Other35 scenario, the FPR is controlled at 0.08%. For the Half-Half Other15 scenario, the FPR is controlled at 0.71%. For the Cholangio35 scenario, FPR is at 7.42%. The reasonable FPR control on scenarios Half-Half Other35, Half-Half Other15, and Cholangio35 are aided by the interim and final futility analysis before pooled efficacy analysis, thus helping to prune original tumor agnostic pool with $\text{ORR} < 15\%$ to the final tumor pool with $\text{ORR} > 15\%$ by excluding those tumor histologies that met the futility criteria from final pooling.

Another aspect to consider is the proportion of mixing nonactive tumor histologies for success on pooled data. For the scenarios Half-Half Other35, Half-Half Other15 and Cholangio35, the proportions of mixing nonactive are 19.8%, 23.5%, and 36.1% respectively. Noticing that these scenarios have a considerable number of nonactive tumor histologies, the pooled efficacy analysis may not be performed at the primary analysis if a large amount (e.g. 50%) of tumor histologies were stopped for enrollment.

Note that the FPR for scenario Global Null is inflated as 18.57% and the scenario Alternative is overpowered with power 1, different alpha levels for testing are investigated in [Table A5](#). An alpha level of 0.005 will lower the FPR under 10% while maintaining strong power for both Alternative and Target scenarios. An alpha level of 0.001 will lower the FPR under 5% while moderately sacrificing the power for scenario Target.

Summary

Based on the operating characteristics of different scenarios, the proposed design outlined in this study will have a control of FPR for Half-Half Other35 (0.08%) and Half-Half Other15 (0.71%), and a moderate control of FPR for Cholangio35 at 7.42%, while the FPR for the Global Null is 18.57%. In addition, it achieves a satisfactory performance in terms of testing power (e.g., above 95% power and proportion of success for scenario Alternative) and selection power (approximately 85% power to select at least 80% tumor histologies for scenario Alternative).

Table A3: Operating Characteristics for Duration of the Trial, Ppn of Success, and Power

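### SAP A.3.3 permits skipping the pooled primary test that SAP 5.2.3.1 and Protocol 9.4.3.1 require, on undefined terms, and the pooled-test operating characteristics do not reflect that option

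*SAP*

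**What the plan says.** SAP 5.2.3.1 sets the primary analysis: "The primary efficacy analysis after the final futility assessment will be performed on the pooled data from all tumor histologies" that did not meet futility. The null hypothesis of an ORR of at most 15% "will be tested at a significant level of 0.025 using one-sided exact binomial test", and the section repeats the commitment: "The test will be performed on the pooled data of all tumor histologies" that survive futility in the Broad Panel Cohort. Protocol 9.4.3.1 agrees: "The primary efficacy analysis will be performed on the pooled data of all tumor histologies" that did not meet futility. None of these statements carries a condition.

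SAP Appendix A.3.3, under FPR and Mixing Nonactive, discusses the scenarios with many nonactive histologies and adds that "the pooled efficacy analysis may not be performed at the primary analysis if a large amount (e.g. 50%) of tumor histologies were stopped" for enrollment.

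Appendix A.3.2 defines the power reported in Table A3: "Power is calculated as the proportion of simulations claiming a success (efficacy) on the pooled data of primary efficacy analysis". The parameter list in A.2 contains no rule for leaving the test out.

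**The concern.** The appendix allows something that the main text of both documents excludes. The permission is loose: 50% is only an example, and nothing says whether the count is out of the 14 listed histologies or the 15 groups including Other, who decides, or what is reported instead. The number of stopped histologies follows from response data that the DRC reviews (SAP 3.2). The DRC also sees all available efficacy data at the final futility assessment, just before the pooled test (SAP 5.2.3.1), and the trial is open-label (SAP 1.5). Whether the primary hypothesis is tested could therefore be settled after responses are known.

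Two things are at stake. An unfavourable primary test could go unrun, with no rule to show that this was planned. And the printed pooled-test power describes only a plan in which the test is always run.

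**Working it through.** **Inputs from the SAP.** N = 200 response-evaluable subjects; cap 30 per histology; futility looks at 60, 100 and 140; stop if Pr(ORR > 25%) < 40% with at least 5 subjects; Other never stopped at an interim; no dropout; peak accrual 5 per week (all A.2). Prevalences from Table A1, scenario rates from A.3.1, and priors from A.1 with μ ~ N(−2.19, 2²).

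**Assumptions.** The ramp-up is in a figure not available here; 8 weeks was assumed (16 was also tried). The prior on heterogeneity was read as centred at τ = 2 with weight 0.75, giving τ² ~ inverse gamma(0.375, 1.5). Half-Half Other15 and Cholangio35 rates come from the scenario text, because their Table A2 rows are broken in extraction.

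**Method.** 4,000 simulated trials per scenario: three interim futility looks, a final futility look, then the one-sided exact test against 15% at 0.025. Monte Carlo standard error is at most √(0.5 × 0.5 / 4000) = 0.008. In variant A, histologies stopped at an interim stay out of the pool; in variant B they are reassessed at the final look. Leaving out the Interim II success rule is harmless: P(X ≥ 50 | n = 100, 15%) is about 2 × 10⁻¹⁶.

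**Step 1: reproduce Table A3 with the test always run. Step 2: apply a skip each time the count of histologies stopped for enrollment reaches the trigger.** The skip columns are variant A; B is nearly the same.

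| Scenario | Table A3 | Always run, A / B | Chance of skip, ≥7 of 14; ≥8 of 15 | Power with skip, ≥7 of 14; ≥8 of 15 |
|---|---|---|---|---|
| Global Null (= FPR) | 0.1857 | 0.169 / 0.213 | 0.97; 0.94 | 0.017; 0.036 |
| Alternative | 1 | 1.000 / 1.000 | 0.011; 0.004 | 0.989; 0.997 |
| Target | 0.9763 | 0.975 / 0.984 | 0.37; 0.22 | 0.631; 0.777 |
| Half-Half Other35 | 0.9966 | 0.998 / 0.998 | 0.95; 0.73 | 0.047; 0.267 |
| Half-Half Other15 | 0.9816 | 0.986 / 0.990 | 0.96; 0.76 | 0.037; 0.237 |
| Cholangio35 | 0.4974 | 0.511 / 0.549 | 0.97; 0.89 | 0.028; 0.093 |

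Variant A matches every Table A3 power within 2 points. Variant B misses Global Null and Cholangio35 by more than that, but it reproduces the selection power in A.3.3 (at least 12 histologies 0.826, at least 10 0.942, all 15 0.295, against 83%, 95% and 29.4%) and the Half-Half mixing figures (0.195 and 0.230, against 0.198 and 0.235). Neither variant matches everything, but the skip results hardly depend on which is used.

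**Step 3: were the tables computed without the option?** Under a rule applied every time, power cannot exceed 1 − P(skip). For Half-Half Other35 that ceiling is 1 − 0.9535 = 0.0465, or 1 − 0.7335 = 0.2665. The printed 0.9966 is far above both, which agrees with the absence of a skip rule in A.2.

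**Step 4: the denominator matters.** Half-Half has 7 nonactive listed histologies: 7/14 = 50%, but 7/15 = 47%. That choice alone moves Half-Half Other35 power from 0.05 to 0.27.

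**Step 5: direction of the error rate.** P(pooled success with the option) = P(success and test run) ≤ P(success). Skipping can only remove pooled successes, so the printed FPRs remain upper bounds however the option is used.

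**The case against.** The strongest reply is that the operative text is consistent. SAP 5.2.3.1 and Protocol 9.4.3.1 agree, the tables describe that plan, and the conflicting sentence is a remark in a simulation appendix. The stops that would trigger it arise at interim looks based mainly on investigator assessment, not from the pooled IRC result. SAP A.3.1 uses Alternative and Target for power, and the Half-Half and Cholangio35 scenarios for futility and FPR. SAP 5.2.3.2 already plans an analysis that includes the futile histologies, so a half-closed trial would still report efficacy. A gate also has merit, since it lowers a Global Null FPR that A.3.3 itself calls inflated.

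Most of this stands, and it limits the point. It does not remove the contradiction or the discretion: the sentence is current text, and the decision would still be taken with response data in hand. The SAP does quote power for a mixed scenario ("The scenario Half-Half Other35 achieves 99% power and 94% proportion of success") in the same appendix section that reserves the option not to test.

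A reader might infer that the reported error rates lose their meaning. They do not, because a skip cannot create a pooled success. If only would-be failures were skipped, both power and FPR would be unchanged; the harm would then be an unreported negative test. A reader might also infer that Tables A3 to A5 fail as a whole. Selection power, FWER, proportion of success and duration do not depend on the pooled test.

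**Conclusion.** The point holds as an unresolved contradiction about whether the primary test is run, with undefined and data-dependent discretion. The figures affected are Table A3 Power, Table A4 FPR and Mixing Nonactive, and Table A5.

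The main cost is in Target, which the SAP uses for power: from about 0.98 to 0.63 or 0.78, depending on the denominator. Half-Half shows a larger fall but is an FPR scenario sitting on the 50% threshold. Alternative, the basis of the sample size, hardly moves.

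These losses are upper limits for a 50% rule applied every time it triggers; the text says only that the test may be omitted. They rest on the assumed accrual ramp, the assumed reading of the τ prior, and stopping by the model rule alone, whereas the DRC weighs all available data. The FPR bound covers the pooled test only, since no replacement analysis is named.

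**What to change.** Delete the sentence from A.3.3. State in SAP 5.2.3.1 that the pooled primary test is run whatever number of histologies stopped, with the all-histology analysis of 5.2.3.2 shown beside it. That companion result matters most when few histologies remain in the pool. The cost is two edits and the loss of a discretionary option; the tables then again match the rule for running the test.

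If the sponsor prefers a gate, write it in 5.2.3.1 as binding, with a fixed count, denominator, decision-maker and fallback analysis, and rerun the pooled-test figures under it. The cost is the rerun and less favourable stated power, chiefly in Target.

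The Amendment 5 history in Protocol Appendix 14 describes the adult primary analysis as complete. If so, the study report should state how many histologies were stopped and whether the option was used.

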Besides the BHM based futility guideline, all available interim data (eg, efficacy, safety, and biomarker data) will be assessed to determine whether enrollment in a given tumor histology should continue, such as the representativeness of biomarker alterations (the expected variant representation by tumor histology based on genomic database assessment). If a tumor histology is deemed futile by the DRC, further enrollment in the histology group will stop; subjects who have been enrolled in the tumor histology group will continue treatment and evaluation as per the protocol. Note that in the primary analysis, a final futility assessment using the same futility guideline as at the interim (i.e, posterior $Pr(ORR > 25\%) < 40\%$) but based on ORR by IRC will be performed for all enrolled tumor histologies as part of the primary analysis to identify the tumor histologies for the pooled primary efficacy analysis (Details in section [5.2.3](#)).

Other details of the planned analysis and efficacy/futility assessment are specified in Section [4-6](#).

Figure 2: Interim Analysis for the Broad Panel Cohort

*At Interim Analysis II, both futility and efficacy will be assessed.

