5.1.1. Level of Significance

In general, statistical inference on the primary endpoint will be tested at 0.025 one-sided level, unless otherwise specified. All interval estimations will be reported using 2-sided 95% CIs.

Multiplicity adjustment for testing the primary endpoint ORR in both Broad Panel Cohort and Core Panel Cohort is based on an error-spending function approach (Spiessens and Debois, 2010). It uses the correlation between the two test statistics in the Core Panel Cohort and the Broad Panel Cohort. The α level for testing the hypothesis in the Core Panel Cohort will use Hwang-Shih-DeCani error spending function with gamma 0 and the information fraction as the ratio of the observed number of subjects in the Core Panel Cohort over the observed number of subjects in the Broad Panel Cohort at the time of primary analysis.

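### The primary test stays at one-sided 0.025 after histologies are selected on the same IRC responses, although the SAP's own Global Null simulation gives an 18.57% false positive rate

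*SAP*

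**What the plan says.** SAP 3.2 says that a last futility assessment, with the interim posterior rule "but based on ORR by IRC will be performed for all enrolled tumor histologies as part of the primary analysis", picks the histologies for the pooled test. SAP 5.2.3.1 confirms that only histologies surviving this step are pooled, and that all available data "will be assessed by the DRC to determine whether a given tumor histology is futile". The null hypothesis of ORR at most 15% "will be tested at a significant level of 0.025 using one-sided exact binomial test", with an ordinary two-sided 95% Clopper-Pearson interval.

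The level is the same elsewhere. SAP 5.1.1: "statistical inference on the primary endpoint will be tested at 0.025 one-sided level, unless otherwise specified". Protocol 9.4.3.1: "Statistical inference on ORR by IRC will be tested at 0.025 one-sided level, unless otherwise specified". The only adjustment is the error-spending split between the Broad Panel and Core Panel Cohorts.

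Appendix A.3.3 reports how the pooled test behaves: "Note that the FPR for scenario Global Null is inflated as 18.57% and the scenario Alternative is overpowered with power 1". It then looks at smaller levels: "An alpha level of 0.001 will lower the FPR under 5% while moderately sacrificing the power for scenario Target". It also says that "the pooled efficacy analysis may not be performed at the primary analysis if a large amount (e.g. 50%) of tumor histologies were stopped for enrollment". Neither a smaller alpha nor this skip clause appears in 5.1.1 or 5.2.3.1.

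**The concern.** The same IRC responses decide which histologies enter the pool and whether the pool beats 15%. Histologies with a lucky run of responses stay and unlucky ones go, so the surviving pool looks better than it is even when nothing works. An exact binomial test and a Clopper-Pearson interval assume a pool fixed without looking at the responses. The overlap arises at the final cut; the interim stops rest mainly on investigator-assessed response.

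A positive primary result would be reported as significant at one-sided 0.025, while the sponsor's own simulation says the procedure succeeds in 18.57% of trials when every histology sits at the null rate. The pooled ORR and its interval are biased upward too, by an amount the SAP does not give. The Japan analysis in A.4 takes over the same futility decisions and declares success if the 95% interval excludes 15%.

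**Working it through.** **1. The SAP's own figures (Tables A3 to A5, 20,000 runs).** Global Null means a true ORR of 15% in all 15 groups.

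- Ratio to nominal: 0.1857 / 0.025 = 7.43.
- Simulation standard error: sqrt(0.1857 × 0.8143 / 20,000) = 0.0027, so chance does not explain it.
- Other scenarios at 0.025: 0.08% (Half-Half Other35), 0.71% (Half-Half Other15), 7.42% (Cholangio35).

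**2. Re-simulation.** Inputs from A.1 to A.3: Table A1 proportions, cap 30, N = 200, looks at 60, 100 and 140 evaluable subjects with a 6-week endpoint, 5 subjects per week at peak, at least 5 subjects for an interim stop, Other exempt at interims, and the final rule applied to all groups. My assumptions: a 12-week accrual ramp (the figure is not shown), IRC and investigator response equal, and tau-squared as inverse gamma (0.375, 0.75). I ran 20,000 Global Null trials and 10,000 Target trials (true ORR 25% everywhere).

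| Alpha | SAP FPR, Global Null | My FPR | SAP power, Target | My power, Target |
|---|---|---|---|---|
| 0.025 | 18.57% | 18.3% | 97.63% | 97.7% |
| 0.005 | 8.50% | 9.2% | 94.56% | – |
| 0.001 | 3.73% | 4.3% | 88.78% | 90.5% |
| 0.0005 | – | 2.7% | – | 87.3% |
| 0.0004 | – | 2.4% | – | 86.4% |

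SAP power at a true 35% is 1 at every tabulated alpha. The other scenarios also agree: Half-Half Other15 power 97.9% (SAP 98.16%), Cholangio35 power 48.6% (49.74%) and FPR 6.7% (7.42%). One check fits less well: at least 12 histologies are selected in 90% of Alternative runs, against about 83% in the SAP.

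**3. Is selection the cause?** Without pruning, the exact test at n = 200 rejects at 41 or more responses and has size 0.0220. In simulated Global Null trials the all-histology test rejects in 2.0% to 2.6%.

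**4. Sensitivity.** A.1 can be read as centring the prior at 2 for tau-squared or for tau. A second, separately coded simulation varied this, and whether histologies stopped at an interim could re-enter: 14.5%, 18.6%, 19.8% and 25.1%. My own variants (the tau-scale prior, no 6-week delay, stopped groups kept out) ran from 12% to 24%.

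**5. Core Panel split.** If the Core Panel is 20% to 70% of the Broad Panel (assumed), gamma 0 gives the Core Panel 0.005 to 0.0175 and leaves the Broad Panel about 0.021 to 0.015. Table A5 gives 14.44% at 0.015. Interpolated at 0.021 it gives 16.35 + (0.001 / 0.005) × (18.57 − 16.35) = 16.8%.

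**6. Bias.** Under Target the pool is non-empty in 99% of runs. The mean pruned-pool ORR is 33% against a true 25%, and the lower 95% limit lies above the truth in 34% of runs. Under the 35% alternative the bias is 1.5 points.

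**7. Skip clause made binding.**

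| Skip the pooled test if | Global Null FPR | Success, Target | Success, Half-Half Other15 (SAP power 98.16%) |
|---|---|---|---|
| 7 or more stopped (half of the 14 that can stop at an interim) | 1.4% | 64% | 3% |
| 8 or more stopped | about 3% to 5% | about 75% to 79% | about 20% to 22% |

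**The case against.** The strongest reply is that nothing is hidden. The SAP calls the rate inflated, tabulates five smaller alphas, repeats 18.57% in its summary, and already commits in 5.2.3.2 to an analysis of all histologies. That is true, but disclosure in an appendix does not make 0.025 the error rate of the test in 5.2.3.1.

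Second, 18.57% belongs to one scenario; the mixed scenarios are lower, and earlier activity in cholangiocarcinoma makes an exact Global Null less plausible. This stands as a limit on how the figure is described. It does not remove the problem: 15% everywhere is the boundary of the stated null hypothesis, and Cholangio35 at 7.42% is still about three times nominal.

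Third, the skip clause, enforced at 8 stopped histologies, brings the Global Null rate close to nominal. That also stands. But the clause is discretionary, sits only in the appendix, and cannot coexist with the Half-Half power claimed in Table A3, whichever cut-off is used.

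Fourth, the DRC weighs all available data, so real selection is not the mechanical rule simulated. That makes the true error rate unknown rather than smaller, and treating the posterior rule as binding is a design change, not mere wording.

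Fifth, the Amendment 5 entry in protocol 10.14 indicates that the adult primary analysis is complete, in which case alpha should not be changed now. The fix below allows for that.

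**Conclusion.** The concern holds. As written, the pruned-pool test does not have a one-sided error of 0.025. By the SAP's own count the error is 18.57% under Global Null, and about 14% to 17% after the Core Panel split. Every variant I tried lies between 12% and 25%, while the unpruned test stays at 2.0% to 2.6%. The main figure rests on the SAP's tables, not on my code.

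The limits are these. The 18.57% applies to the mechanical posterior rule, a single response variable, and the older Table A1 histology list rather than the current Table 3. The replacement level of about 0.0004 to 0.0005 is my estimate (0.0003 to 0.0006 across the second simulation's variants), which is why a rerun is needed.

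**What to change.** **If the primary analysis has not been run.** In SAP 5.1.1 and 5.2.3.1 and protocol 9.4.3.1, replace 0.025 for the pruned-pool test with a level found by rerunning the existing simulation so that the Global Null false positive rate is at most 2.5%.

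- Include the Core Panel test, the Table 3 histologies, and the final posterior rule as binding. Table A5 shows the level must be below 0.001. With the Core Panel at an assumed 30% to 50% of the pool, an overall 0.0005 gave 2.2% to 2.3% under Global Null and 85% to 86% power under Target.
- Report the pruned-pool interval at the matching level.
- State in 5.2.3.1 whether the A.3.3 skip clause applies.

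No extra patients are needed. The costs are a rerun, wording in three sections, and loss of DRC discretion over the final cut. Power at a true 35% stays about 1. At a true 25% it drops below the 88.78% shown for 0.001, to about 83% to 87%. Half-Half Other15 falls from 98% to about 90%, and Cholangio35 from 49% to about 23%.

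**If it has been run.** Do not reset alpha. Report the all-histology analysis of SAP 5.2.3.2 beside the pruned-pool result, and state that the pruned test at 0.025 has a simulated Global Null false positive rate of 18.57%. The cost is one table and one statement.

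The all-histology test should not become the confirmatory one: its power under Half-Half Other15 is about 58%, against 98% for the pruned test.
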